RQ2: Compared to the table, will the risk ladder elicit higher risk perceptions, response efficacy, worry, affective reactions to information, affective attitudes to exercise, and anticipated regret?

Sociodemographic exploratory research questions

RQ3: Will education, race/ethnicity, numeracy, health literacy, and/or graph literacy moderate the effect of risk communication strategy on primary outcomes?

MENTAL IMAGERY

To test whether supplementing the risk calculator with a mental imagery-based self-regulation intervention will increase actual engagement in physical activity over time, and to explore several possible mechanisms.

Primary outcome and exploratory research questions

H5: Engagement in physical activity will increase from baseline to 90-day follow-up only among individuals in the physical activity mental imagery intervention,^[5, 7-9] not in the sleep hygiene imagery active control condition.

RQ5: Will education, race/ethnicity, numeracy, health literacy, and/or graph literacy moderate the effect of mental imagery condition on behavior?

Secondary outcomes and exploratory research questions

H6: Within the physical activity mental imagery condition, increases in activity from pre-intervention baseline to 90-day follow-up will be preceded by the following measures assessed at the week 4 follow-up: action planning, coping planning, action self-efficacy, maintenance self-efficacy, recovery self-efficacy, affective attitudes to exercise, and perceived vividness of imagery.^[5, 7-9, 16]

RQ6: Within the physical activity mental imagery condition, the direction and magnitude of change in activity from pre-intervention baseline to week 1 follow-up will be preceded by the following measures assessed at the survey assessed immediately post-intervention: action planning, coping planning, action self-efficacy, maintenance self-efficacy, recovery self-efficacy, affective attitudes to exercise, and perceived vividness of imagery.^[5, 7-9, 16] Similarly, measures assessed at week 1 will predict change in behavior from week 1 to week 2; measures assessed at week 2 will predict behavior change from week 2 to week 3; and measures assessed at week 3 will predict behavior change from week 3 to week 4.

Eligibility Criteria

RISK CALCULATOR AND MENTAL IMAGERY

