To reduce participant burden, we limit the number of survey questions by adapting single item measures used in nationally representative surveys and in published empirical research. Many items are identical or very similar to the items in Aim 1 and Aim 2, Part 1 of the study. All items for the proposed research, including items that were adapted or developed specifically for Aim 2, Part 2, underwent cognitive testing in either Aim 2, Part 1 or in prior research studies conducted by the [name] Lab. Adaptations to the items intended for use in the text messaging surveys (160-character limit) were made in close collaboration with [name], who was the initial developer of the interventions. Table 1 below provides each of the measures that will be assessed in each part of the survey.

Table 1. Summary of Study Measures, in Order of Completion

Questionnaire Name	Timing	Content
Part 1: Baseline		
Eligibility Screener (Appendix H)	Pre-randomization	Age; ^[23] race/ethnicity; ^[23] education; ^[23] personal diagnosis of the target diseases; ^[24, 25] physical activity behavior; ^[26, 27] and cell phone access (developed in-house)
Risk Assessment (Appendix A)	Immediately following randomization to 1 of 6 conditions in a 3 (risk presentation: text vs. table vs. risk ladder) x 2 (mental imagery: physical activity vs. sleep hygiene) design	Demographic, biological, and behavioral characteristics needed for the risk algorithm ^[28-30]
Baseline Survey 1 (Appendix C)	Immediately following provision of personalized risk information	Comprehension; ^[31] cognitive and affective perceived risk; ^[32] perceived severity ^[33] worry; ^[32] response efficacy; ^[34] action self-efficacy; ^[35] affective reaction to the information; ^[36] affective attitude about exercise; ^[16] anticipated regret; ^[17] intentions to engage in physical activity in the next 90 days; ^[34] numeracy ^[37] ; graph literacy; ^[20] health literacy. ^[38] self-reported health status; ^[24] work schedule; ^[39] sleep behavior. ^[9] Other items intended to be used as preliminary data in future studies examining possible defensive processing of personalized health risk information include: perceived accuracy of information; ^[4, 40] message acceptance; ^[41] defensive processing ^[42] time orientation, ^[43] and spontaneous self-affirmation. ^[32]

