Baseline Survey 2 (Appendices L and M)	Immediately following completion of the mental imagery activity. The specific item wording is tailored based on which mental imagery condition is assigned (i.e., mental imagery vs. sleep), but the constructs assessed are the same for both conditions.	Message acceptance, ^[41] perceived clarity and vividness of images; ^[5, 9] and the following items obtained, developed, or adapted from: ^[5, 6, 9, 34] action plan; coping plan; action self-efficacy; recovery self-efficacy; and maintenance self-efficacy.
--	--	--

Part 2: Text Messaging

Mid-Intervention Text Message Surveys (Appendices X and Y)	1, 2, 3, and 4 weeks after Part 1	Perceived clarity and vividness of images; ^[5, 9] and the following items obtained, developed, or adapted from: ^[5, 6, 9, 34] action plan; coping plan; action self-efficacy; recovery self-efficacy; and maintenance self-efficacy.
--	-----------------------------------	--

Part 3: 90-Day Follow-Up

Follow-Up (Appendix BB)	90 days after Part 1	Comprehension; ^[31] physical activity behavior, ^[26, 27] sleep behavior, ^[9] tobacco use, ^[27] and the same items as in Baseline Survey 2 assessing intentions, action self-efficacy, cognitive and affective perceived risk, response efficacy, anticipated regret, and affective attitudes.
-------------------------	----------------------	---

Note: Race and education will be assessed during eligibility for recruitment stratification purposes only. Baseline Survey 1 excludes characteristics that will be assessed in the Risk Assessment questionnaire.

Statistical Considerations

Preliminary Analyses

We will begin by using descriptive statistics to understand the frequency and distributional properties of all items. For variables with non-normal distributions, data transformations or non-parametric tests will be used for subsequent analyses.

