All hypotheses and research questions will be examined using separate analyses for each outcome variable. Assumptions of each type of test will be checked (e.g., assumptions of normality and homogeneity of variance for ANOVAs). If there are violations, non-parametric tests will be used instead. Sex will be a covariate because there are no valid prediction models for male breast cancer, so men will not be shown a breast cancer risk estimate. The inclusion of other personal characteristics as covariates will be determined by the results of the preliminary analyses. Tests of moderation will be conducted by creating interaction terms between the risk presentation condition or mental imagery condition variables, as appropriate, and the variable assessing the moderator of interest. All statistical tests will be based on list-wise deletion except structural equation models, which can accommodate missing data.

Mediation analyses will be conducted using structural equation modeling (SEM). Full Information Maximum Likelihood estimation (FIML)^[44] will be used to allow the inclusion of missing data. Standardized estimates will be calculated and bias-corrected bootstrapping will be used to obtain the 95% confidence intervals.^[45-48] Criteria assessing model fit will also be examined (e.g., Standardized Root Mean Square Residual $\leq .08$, comparative fit index $\geq .95$, root mean square error of approximation $\leq .06$).^[49, 50] Mediation analyses will examine each construct as an individual mediator first, and then as a multiple mediator model.

Table 2 below describes the analyses that will be conducted for each hypothesis or research question.

Table 2. Overview of Statistical Analyses

	Priority	Statistical test(s)	Outcomes	Predictors/Mediators/Moderators
Risk Calculator				
H1; RQ1	Primary	3 arm ANOVA, 2 planned contrasts (risk ladder vs. text; risk ladder vs. table)	Comprehension, intentions	Predictor: Risk presentation condition
H2	Secondary	SEM	Intentions	Predictor: Risk presentation condition (risk ladder vs. text) Mediators: comprehension, risk perceptions, response efficacy, worry, affective reactions to information, affective attitudes to exercise, anticipated regret
H3	Secondary	3 arm ANOVA, planned contrast (risk ladder vs. text)	Change in physical activity (mins/week at 90 days – mins/week at baseline)	Predictor: Risk presentation condition

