H4	Secondary	SEM	Change in physical activity (mins/week at 90 days – mins/week at baseline)	Predictor: Risk presentation condition (risk ladder vs. text) Mediator: Intentions
RQ2	Secondary	3 arm ANOVA, planned contrast (risk ladder vs.	Risk perceptions, response efficacy, worry, affective reactions to information, affective attitudes	Predictor: Risk presentation condition

table) to exercise, anticipated regret

RQ3 Secondary 3 arm ANOVA Comprehension, intentions Predictor: Risk presentation condition
Moderators: Education, race/ethnicity, numeracy, health and graph literacy

Mental Imagery

H5	Primary	T-test	Change in physical activity (mins/week at 90 days – mins/week at baseline)	Predictor: Mental imagery condition
RQ5	Primary	ANOVA	Change in physical activity (mins/week at 90 days – mins/week at baseline)	Predictor: Mental imagery condition Moderators: Education, race/ethnicity, numeracy, health and graph literacy
H6	Secondary	Regression (physical activity mental imagery condition only)	Change in physical activity (mins/week at 90 days – mins/week at baseline)	Predictors: Week 4 action planning, coping planning, action self-efficacy, maintenance self-efficacy, recovery self-efficacy, affective attitudes to exercise, perceived vividness
RQ6	Secondary	Regression (physical activity mental imagery condition only)	Weekly change in minutes of physical activity, assessed by 4 difference scores: Week1-Baseline; Week2-Week1; Week3-Week2; and Week4-Week3	Predictors: For each weekly behavioral assessment, use the previous week's measures of the following constructs: action planning, coping planning, action self-efficacy, maintenance self-efficacy, recovery self-efficacy, affective attitudes to exercise, perceived vividness.

Sample Size Calculations

We will enroll 500 participants at baseline. This will enable us to test the primary hypothesis for each of the components of the study. This calculation was based on the information below.

RISK CALCULATOR

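### H6 and RQ6 explore mechanisms within the imagery arm without adjusting for motivation before the imagery, so prior motivation can make the constructs appear to predict activity change

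*Combined protocol and SAP*

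**What the plan says.** The Mental Imagery objective includes the aim "to explore several possible mechanisms". In Table 2, H6 and RQ6 are the rows that serve it. Both are secondary regressions confined to the physical activity imagery condition.

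- **H6 predictors:** "Week 4 action planning, coping planning, action self-efficacy, maintenance self-efficacy, recovery self-efficacy, affective attitudes to exercise, perceived vividness". The outcome is the change in weekly minutes from baseline to 90 days.
- **RQ6 predictors:** "For each weekly behavioral assessment, use the previous week's measures of the following constructs", followed by the same seven. The outcomes are four successive differences, from Week1-Baseline to Week4-Week3.
- **Covariates (Main Analyses):** sex is fixed ("Sex will be a covariate because there are no valid prediction models for male breast cancer"). Others are personal characteristics chosen by the preliminary tests. The characteristics itemised under Preliminary Analyses include baseline activity, but no intentions, self-efficacy or attitudes.
- **Timing (Table 1 and Procedure):** Baseline Survey 1 comes just before the imagery component. It measures "intentions to engage in physical activity in the next 90 days", action self-efficacy and affective attitude about exercise. Planning, coping planning, and maintenance and recovery self-efficacy first appear in Baseline Survey 2, given "Immediately following completion of the mental imagery activity".

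**The concern.** Within one arm, randomisation does not balance people who plan a lot against people who plan little. The level of a construct after the imagery mixes what the imagery produced with what the person brought. Someone who arrives strongly motivated may both plan more at week 4 and be more active at 90 days, even if the imagery changed nothing.

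The plan itself expects a link from motivation to behaviour. The Background counts intentions among the cognitions through which behaviour changes. H4 makes intentions the mediator for the same activity-change outcome that H6 uses.

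Because the stated aim concerns mechanisms, a significant coefficient in H6 is likely to be read as a route by which imagery acts, and later interventions may be designed around it. The concern is strongest for H6 and for RQ6's first interval, Week1-Baseline. A stable level of motivation need not predict later week-to-week differences.

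**Working it through.** **1. Size of the arm.** No sample size is given for H6 or RQ6, so the H5 calculation is used. A two-sided t-test with alpha 0.05, 80% power and d = 0.30 needs 176 per arm by the noncentral t, 352 in total, which reproduces the plan's figure. Then 352/0.70 = 502.9, or 503, against the 500 stated. Equal allocation puts 352/2 = 176 in the imagery arm at 90 days, before any missing week 4 texts.

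**2. Assumptions, none of them from the documents.** Let a be the correlation of pre-imagery intentions with each construct, and b their correlation with activity change. No construct has any effect on activity. The settings (a, b) are (0.3, 0.2), (0.4, 0.3), (0.5, 0.3) and (0.5, 0.4).

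**3. One construct at a time.** The induced correlation is r = ab, and the noncentrality of the t-test is r√n/√(1 − r²), with √176 = 13.27.

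| a, b | r | Noncentrality | False-positive rate |
|---|---|---|---|
| 0.3, 0.2 | 0.06 | 0.80 | 12% |
| 0.4, 0.3 | 0.12 | 1.60 | 36% |
| 0.5, 0.3 | 0.15 | 2.01 | 52% |
| 0.5, 0.4 | 0.20 | 2.71 | 77% |

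Simulation agrees to within about two percentage points. If a or b is zero, the rate stays at about 5%.

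**4. All seven together.** Table 2 most naturally reads this way: it lists seven predictors under one regression, and Main Analyses separates analyses by outcome, not by predictor. The text does not settle it. Let ρ be the correlation between any two constructs, assumed to be 0.3-0.5.

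- *Planning coefficient.* The shared bias is divided among the seven. Each standardised coefficient is r/(1 + 6ρ). At r = 0.20 and ρ = 0.3 this is 0.20/2.8 = 0.071, and at r = 0.06 and ρ = 0.5 it is 0.06/4 = 0.015. By simulation, the false-positive rate is about 5-13% over the four settings.
- *Overall test of the seven.* R² = 7r²/(1 + 6ρ).
  - Smallest case (r = 0.06, ρ = 0.5): 7 × 0.0036/4 = 0.0063. With 176 − 8 = 168 residual degrees of freedom, the noncentrality is about 168 × 0.0063/0.9937 = 1.07.
  - Largest case (r = 0.20, ρ = 0.3): 7 × 0.04/2.8 = 0.10, and 168 × 0.10/0.90 = 18.7.
  - The noncentral F gives about 9% and 89%. Simulation gives about 8-89%.

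**5. After adjustment.** With intentions measured without error, all three rates return to about 5%. With reliability 0.8, the one-at-a-time rate is about 5-10% over the same settings.

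**The case against.** The strongest reply is that the analyses claim little. They are secondary, worded as temporal precedence or prediction, and serve an exploratory aim. Formal mediation by structural equation modelling is planned only for H2 and H4. This stands, and it limits the point's weight. It does not remove the need for an explicit statement, because the objective invites a reading in terms of mechanism.

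A second reply is that the plan is not wholly unadjusted. Sex is fixed, baseline activity may enter through the screen, and a change score removes stable differences in activity level. That is correct, but none of these is motivation to change.

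Four stronger readings are tempting, and the documents do not support them:

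- **That prior motivation will distort H6.** Bias needs motivation to be related to both the construct and the activity change. The documents give neither correlation.
- **That the planning coefficient is falsely significant in half or more of trials.** This requires one-at-a-time entry and the larger assumed correlations. Under joint entry the other constructs absorb much of the shared motivation.
- **That the protocol's model makes intentions and action self-efficacy the drivers of action.** The Background says that moving on to action rests on factors outside the motivational stage, and it acknowledges a gap between intending and doing. Support for the intentions-activity link comes from H4 and the Background's remark on health cognitions.
- **That adjustment turns the tested quantities into change since before the imagery.** Table 1 lists no affective attitudes in Baseline Survey 2 or the weekly texts, so at most this holds for action self-efficacy. Even there, the cited item sources differ between surveys, so comparability would have to be shown.

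**Conclusion.** The omission is real. H6 and RQ6 serve the mechanism aim through within-arm regressions with no pre-imagery motivation term, and the covariate rules do not bring one in. The distortion is possible, not certain, and its size depends on how the constructs are entered. Under the assumptions stated, it is large for single constructs and modest for one coefficient in a joint model, but it can again be large for the overall test. Joint entry therefore does not by itself protect a conclusion that these constructs as a group predict activity change.

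Adjustment reduces the problem without removing it. Table 1 shows no pre-imagery measure of planning, coping planning, or maintenance or recovery self-efficacy, so residual confounding would remain. This is a cheap improvement to secondary analyses. It does not touch the primary comparisons.

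**What to change.** In the H6 and RQ6 rows of Table 2, add Baseline Survey 1 intentions, action self-efficacy and affective attitudes to exercise as prespecified covariates, not subject to the significance screen. Add one sentence: these analyses identify predictors of activity change within the imagery arm and do not show that imagery worked through them. It would also help to state whether the seven constructs enter together or singly, since the size of the problem turns on it.

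No new data are needed. The cost is three degrees of freedom and somewhat wider intervals for correlated predictors. Participants may also be lost, because regressions use list-wise deletion and the sample size section allows 10% missing in Baseline Survey 1. If that fell fully on this arm, 176 × 0.90 = 158.4, or about 158, would remain.

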Part 2, SMS/Text Message Intervention and Data Collection. Beginning at 7:00pm on the day the participant completes the Baseline/Part 1 activities, the participant will begin receiving text messages related to the study. The first texts will welcome them to the study and provide information about how to contact the Lab, how to stop the texts from being sent, and how to access the audiorecording to which they were assigned (physical activity vs. sleep). At noon on Mondays, Wednesdays, and Fridays, they will be sent 1 of 3 texts that remind them to practice the imagery presented in the audio recording twice daily for five minutes each time. These reminders will continue for 3 weeks. Each week after the 3rd reminder they will receive a text message based survey. A final text message based survey will be sent one week after the third text message based survey. The content and schedule for the text messages and text surveys are found in Appendices X and Y (Text Message Reminders and Survey- Exercise, Sleep). Each text message length is no more than 160 characters, including spaces, to fit within the universal constraints of SMS messaging protocols. This was done to avoid having 1 intended message being sent in multiple pieces. The total participation time per week is estimated to be approximately 10 minutes. Participants will earn a \$10 gift card to Schnucks for each text message survey they complete. This amount is intended to help offset the cost of text messages for participants who may not have unlimited text messaging.

Part 3, Mailed 90-Day Follow-Up Survey. Ninety days after Baseline/Part 1, participants will receive a final follow-up study survey (Appendix BB) in the mail along with a written survey invitation (Appendix AA). If participants do not complete the first mailed survey, we will follow-up with one reminder call (Appendix Z) and one additional mailed survey. The survey is expected to take approximate 15 minutes. Participants will receive a \$20 gift card for Schnucks for completing the follow-up survey.

Part 4, Follow-Up Phone Call. Within one year of the final follow up period, we may contact up to 20 participants by phone and ask them questions about their experience and thoughts on the study process (Appendix II). If this occurs, the phone call will take approximately 10 to 15 minutes.

Measures

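### Tables 1 and 2 contradict each other on weekly activity minutes (RQ6) and affective attitudes (H6, RQ6), and H6's outcome includes change made before its week-4 predictors are measured

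*Combined protocol and SAP*

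**What the plan says.** **Table 1 (Measures).** The section introduces it by saying "Table 1 below provides each of the measures that will be assessed in each part of the survey", although its title calls it a summary. The text-survey row (weeks 1 to 4) lists clarity and vividness of images plus "action plan; coping plan; action self-efficacy; recovery self-efficacy; and maintenance self-efficacy". The Baseline Survey 2 row lists the same constructs plus message acceptance. Physical activity is named only in the eligibility screener and the 90-day survey; the Risk Assessment row, also at baseline, mentions behavioral characteristics in general terms. Affective attitude to exercise is named in Baseline Survey 1, which comes before the imagery, and in the 90-day row. The 90-day row describes its attitude items as "the same items as in Baseline Survey 2 assessing intentions, action self-efficacy, cognitive and affective perceived risk, response efficacy, anticipated regret, and affective attitudes".

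**Table 2 (Main Analyses).** The RQ6 outcome is "Weekly change in minutes of physical activity, assessed by 4 difference scores: Week1-Baseline; Week2-Week1; Week3-Week2; and Week4-Week3". Its predictor cell opens "For each weekly behavioral assessment" and calls for seven constructs from the preceding survey, affective attitudes among them. H6 regresses day-90 minus baseline minutes on the same seven constructs at week 4. Both are secondary and use only the physical activity imagery arm.

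**Objectives.** H6 states that the baseline-to-90-day increase will be preceded by the week-4 measures. RQ6 is worded as a lagged question, with each survey predicting the next interval's change, and ends at week 4.

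**Procedure, Part 2.** "The content and schedule for the text messages and text surveys are found in Appendices X and Y".

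**The concern.** Two separate problems affect the planned study of how the imagery works.

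First, Table 2 uses variables that Table 1 does not place at the required times. If the surveys had been built to Table 1, RQ6 would have no outcome and H6 would lack one of its seven predictors. A weekly item that was not asked cannot be recovered afterwards, so the check belongs before enrolment.

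Second, whatever the appendices contain, the H6 regression cannot show the time order that H6 claims. A participant who is already more active by week 4 may report more planning and self-efficacy because of it. That early gain is part of the day-90 minus baseline outcome, so an association could be read as the measures leading to the increase when the increase came first.

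**Working it through.** **1. Sample available to H6.** The plan's own figure reproduces. A two-sample t-test with d = 0.30, two-sided alpha .05 and 80% power needs 175.4, so 176, per arm, or 352 in total. Allowing for 30% attrition, 352 / 0.70 = 503, against 500 stated. The activity imagery arm therefore has about 500 / 2 = 250 enrolled and 352 / 2 = 176 planned completers. The documents give no week-4 text response rate. Assuming 60% to 100% among 176 completers gives 176 × 0.6 = 106 up to 176.

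**2. Table 2 needs against Table 1 entries.**

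| Variable | Needed at | Listed in Table 1 at those times |
|---|---|---|
| Activity minutes (RQ6) | baseline, weeks 1, 2, 3, 4 | baseline only |
| Affective attitudes (RQ6) | post-imagery, weeks 1, 2, 3 | none in the Baseline Survey 2 or text-survey rows |
| Affective attitudes (H6) | week 4 | none |
| Other six predictors | post-imagery, weeks 1 to 4 | all |
| Activity minutes (H6) | baseline, day 90 | both |

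Each RQ6 difference score needs at least one value from weeks 1 to 4, so none of the four can be formed from Table 1 as written. H6 has 6 of its 7 predictors. These are counts of table entries, not of lost data.

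**3. The 90-day row.** It attributes six constructs to Baseline Survey 2. All six are in the Baseline Survey 1 row, and only one, action self-efficacy, is in the Baseline Survey 2 row. The reference looks like a slip for Baseline Survey 1. Even if taken literally, it would not put affective attitudes in weeks 1 to 4.

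**4. H6 timing.** Week 4 is day 28. 28 / 90 = 31% of the change window has passed when the predictors are measured, and 62 / 90 = 69% remains. Table 2's H6 row has no term for week-4 activity.

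**5. Illustration on assumptions not in the documents.** Write total change = early + late change, uncorrelated, with s the share of variance that is early. Let each of seven week-4 predictors correlate r = 0.3 with early change and 0 with late change, with correlation 0.5 between predictors. Then:

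- R² with early change = 7 × 0.3² / (1 + 6 × 0.5) = 0.63 / 4 = 0.158.
- R² with the H6 outcome = s × 0.158. For s = 0.5 this is 0.079.

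Simulating the seven-predictor regression at s = 0.5 gives:

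| | n = 176 | n = 106 |
|---|---|---|
| Joint test, p < .05 | about 80% | about 53% |
| Any one named coefficient | about 9% | about 7% |

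At n = 176, at least one of the seven coefficients is significant in just under half of runs. The share s is unknown and drives the result. With s = 0.25 (R² = 0.039) the joint test rejects in about 44% (n = 176) or 26% (n = 106) of runs; with s = 0.75 (R² = 0.118), in about 95% or 75%. Adjusting 90-day minutes for week-4 minutes measured without error brings the joint test back to about 4 to 5%, its nominal level.

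**The case against.** The strongest reply on the first part is that Table 1 is only a summary and the survey items are defined in Appendices L, M, X and Y. The reference in Table 2 to a weekly behavioral assessment suggests that weekly minutes were intended. An omission from a summary table is at least as plausible as an omission from the surveys. That stands: a reader might infer that the items were never collected and that RQ6 cannot be run, and the documents do not support that. What remains is that the two tables cannot both be complete.

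On the second part, week 4 does precede the day-90 reading, and RQ6, if its items are collected, orders the early weeks properly. Both points are fair. They leave the change after week 4 without any planned model that uses the week-4 measures, and they do not make H6's own wording true.

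Two stronger readings should also be set aside. A reader might take the prior effect in Sample Size Calculations (about 20% of unique variance at 4 weeks, d about 1.0) as evidence that much of H6's outcome is early change. It is a between-arm effect; H6 explains differences between people within one arm, and a mean shift shared by the arm adds nothing to that variance. A reader might also expect any named measure to appear significant by this route. A single predictor analyzed alone would be, in about 81% of trials at n = 176 under the same assumptions, but Table 2 lists seven predictors in a regression, where each coefficient is significant in only about 7 to 9%.

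**Conclusion.** The point holds in two limited parts.

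- **Tables.** Tables 1 and 2 contradict each other on activity minutes at weeks 1 to 4, and on affective attitudes after the imagery and at weeks 1 to 4. This rests on the text alone and is certain as a contradiction. Whether any data would be lost cannot be judged without the appendices.
- **H6.** The regression can show an association between week-4 measures and the 90-day change, but not that the measures came before the whole increase. About 31% of the window precedes them, and the model does not separate early from later change. How often this would mislead depends on the early share of within-arm change variance, which the documents do not give; the 80% and 53% joint-test figures are illustrations under the stated assumptions.

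Both analyses are secondary. H1, H5 and the sample size are unaffected. The changes should be made because the data check has to come before enrolment and the H6 correction is cheap.

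**What to change.** **Before enrolment, reconcile Tables 1 and 2 against Appendices L, M, X and Y.** Correct the 90-day row's reference to Baseline Survey 2 in either case.

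- If the items are present, add them to Table 1.
- If they are not, add short activity-minutes and affective-attitude items to the text surveys and the attitude item to Baseline Survey 2. Otherwise delete RQ6 and run H6 with six predictors.

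**For H6**, keep the baseline-to-90-day regression but report it as an association and drop the claim that the measures preceded the increase. If week-4 minutes are collected, add one secondary model of 90-day minutes on the week-4 measures, adjusted for week-4 minutes. State that it addresses change after week 4, a narrower question than H6. If week-4 minutes are not collected, report the association only.

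**Cost.** If the items exist, this is a table correction, a wording change and at most one extra model. If they do not, it means two short items per text survey within the 160-character limit, one paper item, slight participant burden, and brief cognitive testing, since the plan says "All items for the proposed research, including items that were adapted or developed specifically for Aim 2, Part 2, underwent cognitive testing". The added model loses further cases, because "All statistical tests will be based on list-wise deletion except structural equation models, which can accommodate missing data". It also adjusts a mailed paper outcome for a text-message measure, and it removes the early-change association only as well as week-4 minutes are measured.
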